4. STUDY DESIGN

4.1 OVERALL DESIGN

This study is a pilot, three-session, parallel-arm study with transcranial alternating current stimulation (tACS), electroencephalography (EEG), and magnetic resonance imaging (MRI) to understand the causal role of delta-beta coupling in goal-directed behavior in participants with major depressive disorder (MDD) and symptoms of anhedonia. Participants that request to be in the experiment will provide verbal, documented consent to undergo a phone screening to assess that the participant meets exclusion/inclusion criteria. Then, participants will complete demographic and self-report clinical assessments via REDCap: Patient Health Questionnaire-8 (PHQ-8) with the suicide question removed (Kroenke, Spitzer et al. 2001) and the Snaith Hamilton Pleasure Scale (SHAPS) (Snaith, Hamilton et al. 1995). Participants that have a PHQ-8 greater than or equal to 8 will be invited to participate in the

study. Also, participants will be stratified based on their SHAPS score (50% > 33 on the SHAPS and 50% ≤ 33). Stratification is conducted to ensure a representative spread in anhedonia scores since we are interested in the relationship between anhedonia and goal-directed behavior. Thus, some participants will not be invited to participate if we have already completed sessions for 24 participants within their median split. The value of 8 for the PHQ-8 is used to help ensure that participants will meet criteria for MDD; thus, improving the feasibility of the study. The value of 33 for the SHAPS was the median SHAPS score from our previous experiment in participants with MDD, and is consistent with findings from other groups. While the PHQ-8 and SHAPS are used to determine eligibility (SHAPS is exclusionary only if a stratum is full), additional self-report clinical assessments are administered for exploratory analyses.

The first session will be a virtual clinical assessments session. Participants will provide verbal consent including a brief verbal assessment of understanding of study procedures. Next, participants will complete two assessments on REDCap while being monitored in a virtual session: the PHQ-9 and must score at least a 10 to proceed with the full session, and the SHAPS is used to check if their stratum is full for randomization purposes. After passing this additional screening, self-report clinical assessments will be completed on REDCap while being monitored: Behavioral Activation System and Behavioral Inhibition System (BIS/BAS) (Carver and White 1994), Temporal Experience of Pleasure Scale (TEPS) (Gard, Gard et al. 2006), the State-Trait Anxiety Inventory (STAI) (Spielberger 2010), Beck Depression Inventory 2 (BDI-II) (Beck and Beamesderfer 1974), and Ruminative Responses Scale (RRS) (Nolen-Hoeksema, Larson et al. 1999). In addition, participants will undergo clinician-report assessments that will be entered onto REDCap: the Mini International Psychiatric Interview for the DSM-V (MINI) (Sheehan, Lecrubier et al. 1998), Hamilton Depression Rating Scale (HAM-D) (Hamilton 1960), Columbia-Suicide Severity Rating Scale (C-SSRS) (Posner, Brown et al. 2011), and the Maudsley Staging Method (MSM) (Donaldson, Poon et al. 2009). Eligibility for the experiment is then determined by a MINI diagnosis of MDD, exclusion based on a present moderate to severe substance use disorder or alcohol use disorder, a history of severe substance use disorder or alcohol use disorder, or a diagnosis of psychosis or psychotic features. In addition, the participant must have low suicide risk as determined by the C-SSRS (see Inclusion/Exclusion criteria above). In the event that a participant has active plans to commit suicide, an adverse event is recorded, an acute psychiatric assessment is conducted by our medical monitor, [name], who is a clinical psychologist at UNC-CH, and participation is terminated. In the case that the person does not see anyone for their depression, [name] will assist the participant in seeking medical care. [name] (Principal Investigator, mood disorders expert) will be available as well, in any instances where [name] is unavailable for acute assessment.

In the second session, participants provide written consent to participate in the study. Then, participants are randomized into one of three arms of the study: delta-beta tACS, control tACS in theta-gamma, or active sham. Randomization is stratified by SHAPS level such that there are an equal number of participants that are high anhedonia (SHAPS > 33) and low anhedonia (SHAPS ≤ 33). We expect that of the 48 participants in the final dataset, there will be 8 from each of the 6 groups (3 stimulation conditions by 2 anhedonia levels). Two 4.5 by 4.5 centimeters stimulation pads are applied to the scalp over the left hemisphere anterior and ventral to F3 and posterior and ventral to C3, and a 5 by 7 centimeters stimulation pad is applied centered over FCz in an anterior to posterior direction. Prior to any task performance, participants under eyes-closed and eyes-open resting-state while fixating on a central point on the monitor. Participants complete titration of the difficult of the EEfRT. Then, participants perform 4 blocks of the EEfRT during the collection of EEG. After each block of the EEfRT, there is a 2 minute eyes-open resting-state scan. Next, participants receive tACS during performance of the EEfRT. Delta-beta tACS, theta-gamma tACS, or sham-tACS is received during task performance. Stimulation is turned off between blocks, and eyes-open resting-state EEG is acquired. The total amount of stimulation is approximately 40 minutes for 8 blocks that

each last approximately 5 minutes. After tACS, participants complete a stimulation side effects questionnaire and a blinding questionnaire. A blinding questionnaire is completed by the experimenter. The blinding questionnaire is a single question that asks whether the participant receive stimulation or placebo, and then asks the participant to provide an explanation for their response. Based on the results of the stimulation side effects questionnaire, a structured adverse events interview is conducted to acquire more information regarding any side effects that were selected to be "very high" by the participant.

[figure not shown]
For the third session, participants are instructed to arrive at the Biomedical Research Imaging Center (BRIC) in Marsico Hall on UNC-CH campus. Participants are instructed to arrive at the facility 30 minutes early to ensure that they are ready to go into the MRI for the 60-minute allotted timeslot. During the 60 minutes of scanning, a 5-minute structural MR is acquired, 10-minutes of functional MR scans during the eyes-open resting-state are acquired, and the remaining time is used to complete as many blocks of the EEfRT as possible. Completion of the MRI session is not required for the dataset to be considered a complete dataset. These additional data acquisitions enable exploratory analyses that will be used to design future studies.

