5. STUDY POPULATION

5.1 INCLUSION CRITERIA

In order to be eligible to participate in this study, a participant must meet all of the following criteria:

- Between the ages of 18 and 65
- Able to provide informed consent
- Have normal to corrected vision
- Willing to comply with all study procedures and be available for the duration of the study
- Speak and understand English
- Low suicide risk as determined by both the Mini International Neuropsychiatric Interview (MINI) for the DSM-5 (assessment of suicidal ideation by the Columbia Suicide Severity Rating Scale (C-SSRS; Ghahramani et al., 2015)) and by the Hamilton Depression Rating Scale (HAM-D; less than 3 for the suicidality item).
- Negative pregnancy test for female participants
- PHQ-8 greater than or equal to 8 prior to the first session
- PHQ-9 greater than or equal to 10 at the start of the first session
- A diagnosis of major depressive disorder on the MINI

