5.4 SCREEN FAILURES

In the design of this study, initial phone screening procedures should identify the majority of participants who could potentially become screen failures if consented to participate in the clinical trial. However, the phone screening process does not necessarily account for all exclusion criteria. After the phone screening, each participant is provided with a link to complete two online assessments via REDCap: the Patient Health Questionnaire (PHQ-8, without the suicide question) and the Snaith-Hamilton Pleasure Scale (SHAPS). Participants must have a PHQ-8 greater than or equal to 8, because this will help to ensure that participants will be diagnosed with MDD during session 1. Also, the stimulation is stratified based on SHAPS (>33 or ≤33). Thus, if 24 participants have completed either of the stratum, then participants within that stratum will not be eligible. In the case that a participant meets these criteria, there is still a chance that the first interview reveals that they do not meet study criteria. The study personnel completing the interviewing process will clearly explain why the participant does not meet criteria. However, in the case that a participant does not qualify based on suicide risk, procedures will be followed to ensure participant safety.

At the first session and after obtaining participant informed consent, the HAM-D will be administered, which contains a question related to suicidal thoughts/actions. If someone answers greater than 2 on the HAM-D (i.e., either "suicidal ideas or gesture" or "attempts at suicide") and indicates intent based on the C-SSRS, their participation in the study will be immediately stopped and [name] (Co-I, responsible for participant safety) will be contacted for acute assessment. In the case that the person does not see anyone for their depression, [name] will assist the participant in seeking medical care. [name] (Co-Investigator, mood disorders expert) will be available as well, in any instances where [name] is unavailable for acute assessment.

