Assessment may include facilitating contact of the participant with their psychiatrist/primary care physician to establish a plan for safety, continued care, and follow-up. If the participant does not have an established provider, [name] will assist the participant in establishing care. If at any point in the assessment, the participant is deemed to be an imminent risk of harm to self or others, study personnel will Department for further care. In any instances where [name] is unavailable, [name] will be available to assist the participant. [name] will be the final arbitrator in case anything (e.g., eligibility, safety) is unclear during this process. [name] and the researcher will defer to [name] in those instances.

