8.2 SAFETY AND OTHER ASSESSMENTS

1. The Columbia Suicide Severity Rating Scale (C-SSRS) (Posner, Brown et al. 2011) will be administered by trained research personnel at the first session to thoroughly assess suicide risk. If a participant reports experiencing either suicidal ideation or suicidal behavior, research personnel will collect more information from the participant to deliver to either [name] or [name]. Clinical personnel will decide if an acute assessment is required. Acute assessment may include facilitating contact of the participant with their psychiatrist or primary care physician to establish a plan for safety, continued care, and follow-up. If the participant does not have an established provider, [name] or [name] will assist in establishing a care plan. If at any point during the assessment, the participant is deemed an imminent risk of harm to self or others, study personnel will enlist the aid of campus security to ensure that the participant is safely escorted to the Emergency Department for further care. [name] and/or [name] will decide if participation should be stopped after the acute assessment. If an acute assessment is required, then participation will be halted.
2. A structured interview probing for the experience of adverse events based on the responses from the stimulation side effects questionnaire will be completed after stimulation on the second session. [name], [name], or [name] will use the completed interview to assess the severity of the adverse event and its relationship to the study intervention.
3. A stimulation side effects questionnaire will be administered at the end of each stimulation session. This tool will be used as a safety measure and to collect data on the participant's experience. A similar questionnaire was used in a previous study (IRB# 13-2995) to determine ability to successfully blind the participants using sham transcranial current stimulation.

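### Section 8.2 answers imminent suicide risk with a campus-security escort, but the session in which suicide risk is assessed is virtual, and no readable text has staff record where the participant is.

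*Combined protocol and SAP*

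**What the plan says.** **Format of Session 1.** Section 4.1: "The first session will be a virtual clinical assessments session". The payment text in 5.5 also calls it virtual, and 8.1.4 has the PHQ-9 completed before the first in-person session.

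**Order within Session 1.** The PHQ-9 and SHAPS come first. On the PHQ-9 a participant "must score at least a 10 to proceed with the full session". The remaining self-reports and the clinician interviews follow.

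**Where suicide risk is assessed.** The inclusion criterion in 5.1 begins "Low suicide risk as determined by both the Mini International Neuropsychiatric Interview (MINI) for the DSM-5" and goes on to the C-SSRS and the HAM-D suicidality item. Section 8.2 says that the C-SSRS "will be administered by trained research personnel at the first session to thoroughly assess suicide risk". Section 5.4 says: "At the first session and after obtaining participant informed consent, the HAM-D will be administered".

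**Response to imminent risk.** The same item of 8.2 that schedules the C-SSRS says that, if imminent risk is found at any stage of the assessment, "study personnel will enlist the aid of campus security to ensure that the participant is safely escorted to the Emergency Department for further care". The corresponding sentence in 5.4 reads, in the available text, "study personnel will Department for further care"; the words stating the action are lost.

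**Other responses.** These are acute assessment by the medical monitor with a named backup (4.1), contact with the participant's own psychiatrist or primary care physician "to establish a plan for safety, continued care, and follow-up" (8.2), referral to UNC Psychiatry (2.3.1), and halting participation (4.1, 5.4, 8.2).

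**The concern.** A campus-security escort presupposes a person whom campus security can reach. A participant on a video call may be at home or elsewhere. If that person is judged to be in immediate danger, staff following 8.2 have a transport instruction written for someone on campus. They may also not know where to send help, since no readable section asks them to find out.

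What is at stake is participant safety in a situation that the protocol itself foresees. Section 2.3.1 puts the suicide rate in MDD at about 20 times the average, and Session 1 is where people not yet cleared for suicide risk are first asked about it. No estimate, test or endpoint depends on this.

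**Working it through.** No power, alpha or sample-size figure bears on the point. The check sets the sections side by side.

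**1. Does the first session in 8.2 mean the virtual one?** The document numbers sessions inconsistently: 6.4, 7.1, 9.3 and 9.4.5 appear to use session 1 for the stimulation visit. Section 8.2 does not. Its next item places the post-stimulation interview at the second session, so its first session is the clinical assessments session. The schedule in 1.3 agrees, with the C-SSRS under Session 1 (Clinical Assessments). Sections 4.1 and 5.5 call that session virtual. One entry points the other way: the schedule marks written consent at Session 1. However, 4.1 gives verbal consent there and written consent at the second session, and 10.1.1.2 has the paper form signed at the first visit to the lab. The virtual reading stands.

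**2. Where are the suicide-risk instruments scheduled?** From the schedule in 1.3:

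| Instrument | Named for suicide risk in 5.1 | Online screen | Session 1 (virtual) | Session 2 | Session 3 |
|---|---|---|---|---|---|
| MINI | yes | no | yes | no | no |
| C-SSRS | yes | no | yes | no | no |
| HAM-D | yes | no | yes | no | no |

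The count is 3 of 3 at Session 1 and 0 of 3 elsewhere. The C-SSRS row appears twice, both times at Session 1, and is counted once. The PHQ-9 is also a Session 1 item. Section 8.1.4 describes it only as a screening tool, and its suicide item is inferred from the label of the PHQ-8 as the version without that question. Including it gives 4 of 4, with the same conclusion. The online screen uses the PHQ-8, so no scheduled suicide-risk instrument precedes the virtual session.

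**3. Which responses work for a remote participant?**

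| Response | Section | Works remotely? | Gets the person to emergency care? |
|---|---|---|---|
| Acute assessment by a clinician | 4.1, 5.4, 8.2 | yes | no |
| Contact with own provider, safety plan | 2.3.1, 5.4, 8.2 | yes | no |
| Referral, help establishing care | 2.3.1, 4.1, 5.4, 8.2 | yes | no |
| Campus-security escort | 8.2 | not as plainly read | yes, if on campus |
| Imminent-risk action in 5.4 | 5.4 | text lost | text lost |

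There is one legible transport step, and it is tied to the campus. None of the rows that work remotely moves a person to emergency care.

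**4. Is the participant's location recorded?** No readable section has staff ask for or record it at Session 1.

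**5. Who is exposed?** Everyone who reaches the Session 1 assessments. That number is not given, because a PHQ-9 below 10 ends the session before the interviews. The enrolment ceiling of 100 in 9.2 does not supply it. How many would be at imminent risk is not given either.

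**The case against.** **The absence falls where the text is damaged.** Section 5.4 governs suicide risk found at the first session, and its imminent-risk action is unreadable. A reader might infer that the plan has no remote emergency step at all. The documents do not support that. Lost words are not missing from the plan, section 10.1.5 is listed in the contents but is not in the readable text, and staff also follow written SOPs (10.1.8) and the approved IRB application (10.1.7.1), which are not available here. The surviving end of the 5.4 sentence resembles 8.2, which suggests the same step without proving it. This objection stands as a limit, but it does not make the legible rule in 8.2 fit the session to which 8.2 applies it.

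**Campus security could be asked for help by phone.** The wording sets a goal, safe arrival, and nothing defines how far campus security can act. That is fair, so the mismatch is a plain reading and not a certainty. Even on the generous reading, staff would need the participant's location.

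**Much of the response already works remotely.** This is correct: the participant is monitored live, and assessment, provider contact and referral need no physical presence. Staff already telephone participants for screening, so confirming a call-back number adds little. The gap narrows to location and emergency transport.

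**The size is easily overstated.** A reader might take the 48 analysed participants as the exposed group. Those 48 must have been cleared as low risk, so they are not the people who would need the step. A reader might also use the expected recruitment split in 5.5 between Chapel Hill/Carrboro and Durham/Raleigh to estimate how many are off campus. Recruitment area says nothing about where someone is during a call, and a Chapel Hill resident at home may be just as far from campus security's reach.

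**Conclusion.** The point holds in a narrow form and should be fixed. Section 8.2 attaches a campus-based transport step to an assessment conducted remotely, and all three instruments that 5.1 names for suicide risk are given only at that virtual session. This is a stated rule that does not fit its setting, not merely an omitted detail. No readable text has staff record where the participant is.

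The conclusion rests on two readings: that the first session in 8.2 is the virtual clinical assessments session, which 1.3 and 4.1 support, and that campus security serves people on campus, which is the plain meaning but is not defined. It is limited by the damaged 5.4 sentence and by SOPs and an IRB application that cannot be seen.

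The size cannot be given as a number of people. Those concerned are people being screened, and the number at imminent risk is unknown. The escort remains suitable for the in-person sessions, where risk may still surface. Neither the virtual format nor the instrument schedule is in question.

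**What to change.** 1. Keep the campus-security escort in 8.2, and state that it applies to in-person sessions.
2. At the start of virtual Session 1, before the PHQ-9 and the interviews, have staff record the participant's current physical location and a call-back number.
3. Add to 8.2 that, for a remote participant at imminent risk, staff keep the participant on the call, contact emergency services for the recorded location, and notify the responsible clinician. If an SOP or the IRB application already says this, cite it in 8.2 instead.
4. Make the same change in 5.4 only if its full text contains the campus-security step.

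The cost is one form field and a short amendment with IRB approval. Sample size, endpoints and analyses are unchanged.

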4.2 SCIENTIFIC RATIONALE FOR STUDY DESIGN

This study is a double-blind, randomized, sham-controlled interventional study. The choice of double-blind and randomization is important for the integrity of our data, especially for the clinical assessments. All individuals involved with data collection (as well as all randomized participants) will be blind to the participant assignment until all data has been collected. This will reduce implicit and explicit bias in the data collection process. In this study, participants will be randomized in to one of three arms: active sham (i.e., placebo) stimulation, delta-beta tACS, or theta-gamma tACS. This is a follow-up to two of our previous studies. One study delivered this same form of stimulation in participants during a cognitive control task, which is different from the reward-based decision-making task described here. This study used a similar task design in which intermittent resting-state EEG found that delta-beta tACS and theta-gamma tACS increased the targeted neural activity and modulated behavior associated with the targeted neural activity. In this experiment, participants and researchers were successfully blinded to which stimulation condition they received. Furthermore, this previous study was a crossover design and, thus, a parallel arm design is even more likely to be double-blind because participants only receive one form of stimulation. A second study recorded EEG during the EEfRT in patients with MDD. This study found that participants with MDD and higher symptoms of anhedonia demonstrated reduced goal-directed behavior and reduced delta-beta coupling. This preliminary data provides strong evidence that stimulation delivered in a delta-beta pattern should be beneficial to behavioral performance. Furthermore, this study serves as a target engagement study and future studies may use these results to develop interventions to treat symptoms of anhedonia in MDD.

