6.3 MEASURES TO MINIMIZE BIAS: RANDOMIZATION AND BLINDING

Randomization

[name], a [name] Lab member, will oversee the randomization of 48 6-digit codes, which will be used by the experimenters. These codes are directly linked to which treatment participants receive

(sham/placebo or 10 Hz tACS at 1 mA) and will be entered into the MATLAB script. 24 codes are generated for each of the anhedonia stratum. In addition, 12 codes will be generated (6 extra codes for each stratum) in the event that a participant is randomized but discontinues the study. Thus, data will be collected until we reach our target of 48 participants, but there will be no bias towards completion for the different arms (in the unlikely event that one of the arms has more dropout than the others).

The assignment of each participant cannot be determined by looking at the codes (e.g., codes are not sequential, code assignment is not based on "odd/even" numbers). Thus, the study is both randomized and concealed by virtue of using random numbers generated by a computer. [name] has no other responsibility in the study other than providing these randomized codes. If [name] leaves the [name] Lab, another equivalent researcher who does not work with human participants will perform this task.

Blinding

This study is designed to be double-blind. This means that the participant and the researchers are unaware of each participant's assignment until the completion of all data collection. This is accomplished using the randomization codes described above. Furthermore, this study utilizes an active sham stimulation. This means that the active sham condition includes some stimulation, mimicking the skin sensations associated with tACS. In our previously concluded trial, participants in the delta-beta tACS, theta-gamma tACS, and active sham groups responded similarly to the blinding questionnaire, indicating that our active sham stimulation successfully blinded the participants.

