9.4 STATISTICAL ANALYSES

9.4.1 GENERAL APPROACH

All testing described below assumes a significance threshold of $p = 0.05$. Analyses will be deemed to be statistically significant if the p -value is less than this threshold. An analysis that does not exceed this threshold will be considered inconclusive. Continuous data will be described using means, standard deviations, and confidence intervals, while categorical data will be described using counts/percentages.

There may be additional covariates included in the analysis. Data will be assessed for normality and, if deemed necessary, corrective procedures will be applied (e.g., log normalization). Based on our previous dataset, we expect that the variables used here will be approximately Gaussian. However, if the distribution of a variable displays a skewed tail and a test for normality fails, then it is justified to use a corrective procedure. This correction will be applied upon consideration of the variables themselves, and not based on the result of the intended analysis.

Data will be collected until 48 participants complete the first session and all data is usable. Given that there is only a single session, we expect to have complete data and all analyses will include the full participant pool. However, if there are technical errors that are not caught in time, then the affected analyses may have less participants. In this scenario, the data for a participant is then completely removed from the analysis. We emphasize that lost data is typically of greater concern for longitudinal and multi-session studies. If a subset of participants does not complete the second session in this experiment, then only the analysis of exploratory outcome 2 will be affected.

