10.1.7.1 THE CAROLINA CENTER FOR NEUROSTIMULATION MONITORING PLAN

The latest version of the approved IRB application for this clinical trial will be followed at all times. This responsibility falls in the hands of the trained research personnel. If at any time there is a deviation from protocol, the deviation from protocol log will be filled out. All team members will be trained on how and when to use this log. Deviations will be sent to IRB every 4-6 weeks (if necessary).

Data will be verified for completeness following every study session and all data will be entered into REDCap, a secure online database. After a participant has completed their participation (full completion through the 2-week follow-up visit or because they withdrew prior to completion), data will be rereviewed for completeness and accuracy. After all data has been collected, data will be re-reviewed by another lab member who was not involved with the data collection process.

AE and SAE are clearly defined in the Master Protocol. Documents of AE and SAE can be found in the study binder on file within [name]. It is responsibility of trained research personnel to report all events to the PI. Reporting of AEs and SAEs is described within **Section 8.3**.

The PI and Co-I will have read-only access to the REDCap database. This allows the PI and Co-I to view reports that provide information on any missing data on an individual participant basis, but does not allow them to add, change or input any data.

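### The blind may end when data collection ends, while late technical removals and added covariates are still undecided, so those choices can be made with the arms known

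*Combined protocol and SAP*

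**What the plan says.** Two sections set the end of the blind. Section 4.2 says that those involved with data collection, and all randomized participants, "will be blind to the participant assignment until all data has been collected". Section 6.3 defines double-blind more broadly, with the participant and the researchers "unaware of each participant's assignment until the completion of all data collection".

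Section 9.4.1 contains decisions that can fall after that point:

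- **Removals.** It allows that "if there are technical errors that are not caught in time, then the affected analyses may have less participants", and in that case "the data for a participant is then completely removed from the analysis". It gives no list of qualifying errors, no decision maker and no deadline.
- **Covariates.** Further covariates may enter the analysis. None is listed and no selection rule is given.
- **Transformations.** These are allowed when a variable has a skewed tail and fails a normality test (not named), with the limit that "This correction will be applied upon consideration of the variables themselves, and not based on the result of the intended analysis".

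Section 10.1.7.1 describes three data checks: after each session, after each participant finishes, and a last one. On the last it says: "After all data has been collected, data will be re-reviewed by another lab member who was not involved with the data collection process".

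Section 9 assigns the analyses to a person without saying whether that person is blind to arm. Neither the statistical section nor the data-handling sections mention a database lock or a blinded data review.

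**The concern.** Blinding protects an analysis only while the choices that shape it are still open. Here the stated blind may lapse at the end of collection, yet who is in the analysis and what is adjusted for can still be settled afterwards. Anyone deciding whether a recording is too faulty to keep, or whether a covariate belongs in the model, could then know the arm.

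With 16 participants per arm, one or two such decisions can move the result. The report could still correctly call the trial double-blind under the protocol's own definition, and a reader could not tell whether exclusions were decided with the arms known. Section 4.2 says that future studies may build interventions on these results, so any such bias would carry forward.

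**Working it through.** The plan gives no figure on this point, so there is nothing to reproduce. The check has two parts: the order of events, then the size of the exposure.

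**1. Order of events**

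| Step | Where | Timing | Tied to a point before unblinding? |
|---|---|---|---|
| Blind may end | 4.2, 6.3 | Collection complete | n/a |
| Session and participant checks | 10.1.7.1 | During collection | Yes, in effect |
| Final re-review | 10.1.7.1 | After collection | Not stated |
| Removal for late technical error | 9.4.1 | When found | No |
| Added covariates | 9.4.1 | Not stated | No |
| Transformation | 9.4.1 | Not stated | No, but may not follow the result |

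The end of the blind and the final re-review share one trigger, and no order between them is given. The gap is therefore a permission: the text allows arm-aware choices but does not schedule them.

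**2. Size, on the planned test**

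Inputs: 48 participants in three arms (9.2), so 48/3 = 16 per arm, matching 2 × 8 in section 4.1; alpha 0.05 (9.4.1); time-by-stimulation interaction followed by Tukey's test (9.4.2).

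With two time points, the interaction test equals a one-way F test on the change score d (during minus before). This leaves out the SHAPS covariate:

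F = [Σ n_j (mean_j − grand mean)² / 2] / MSE, where MSE = Σ Σ (d_ij − mean_j)² / (n − 3), on 2 and n − 3 degrees of freedom.

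Tukey for delta-beta against sham: q = (mean_DB − mean_S) / √[(MSE/2)(1/n_DB + 1/n_S)], referred to the studentized range for three groups.

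Assumptions not in the documents: independent normal change scores with no true effect, and removals chosen with full knowledge of arm and outcome. The lowest delta-beta change scores are removed, and where stated the highest sham score. Two separate simulations (the first with 20,000 replicates) gave:

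| Removed (delta-beta, sham) | Omnibus F, p < 0.05 | F, then Tukey favouring delta-beta over sham |
|---|---|---|
| 0, 0 | 5.0%, 5.1% | 0.9%, 0.8% |
| 1, 0 | 6.2%, 6.4% | 2.1%, 2.1% |
| 2, 0 | 9.9%, 9.9% | 4.4%, 4.3% |
| 1, 1 | 9.9%, 10.0% | 5.0%, 4.8% |

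A further simulation of the same F test used 3,000 replicates, a before/during correlation of 0.5 as in section 9.2, and an assumed mean of 55% and SD of 15 points. Monte Carlo standard error at the fixed-analysis rate: √(0.055 × 0.945 / 3000) ≈ 0.004.

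- Fixed analysis: 5.5%.
- One participant removed without regard to arm: 5.6%. Blind removal does no harm.
- Better of raw and log scale: 6.5%. Transformation is a minor exposure.
- Trying every single removal among the 48 and keeping the smallest p-value: 13.6%. This is open searching on the result, a stronger abuse than the table models.

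The effect of covariate choice was not simulated, because the plan names no candidates.

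**The case against.** The strongest reply is that the plan already narrows the window. Section 9.4.1 continues collection until 48 participants have finished with usable data, so usability is judged mostly while the blind holds. Section 10.1.7.1 checks data after every session and again when each participant finishes. Only errors missed by those checks remain, and the plan expects complete data. Removal is tied to technical error, which does not license choosing by outcome. All of this stands. It makes the exposure small, but it does not say who decides the remaining cases or that the decision comes before the key is opened.

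Some stronger readings are tempting, and the documents do not support them:

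- A reader might infer that the codes are opened before the final re-review. Sections 4.2 and 6.3 set a minimum duration for the blind; neither schedules release of the key, and 10.1.7.1 is silent on the order.
- A reader might infer that the final re-reviewer can exclude participants. Section 10.1.7.1 gives no such power.
- A reader might count the coupling calculation among the open choices. Section 9.4.3 fixes the frequency bands, the regions, the Hilbert transform and the normalization against shifted data.
- A reader might size the problem with a two-arm t-test of delta-beta against sham. That gives one-sided rates of about 2.4%, 5.4%, 9.8% and 11.7% for the four rows above, but it is not the planned test. The F-then-Tukey rates are less than half as large.

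**Conclusion.** The concern holds as a gap in a stated rule. The assignment may be released when collection is complete, while late technical removals and added covariates, and to a lesser degree transformations, can still be undecided. The documents do not show that any such choice will be made with arms known.

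As a worst case for the removal patterns modelled, the omnibus type I error rises from about 5% to 6% with one delta-beta removal, and to 10% with two or with one from each of delta-beta and sham. The false-positive rate for delta-beta over sham rises from about 0.8% to 2%, 4% and 5%. These figures assume fully arm-aware, outcome-driven selection, normal change scores and no SHAPS covariate; they do not predict what this trial will do. The secondary outcome has the same model in section 9.4.3, so the same figures apply to it under the same assumptions. The change is worth making because it costs little beforehand and cannot be made once the key has been opened.

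**What to change.** In sections 4.2 and 6.3, replace the end of data collection as the unblinding point with the following: the assignment is released only after the final re-review in 10.1.7.1 is done, the list of exclusions for technical error, the covariates and any transformations are documented, and the dataset is locked.

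The code holder in section 6.3, who has no other role in the study, keeps the key until then. Section 9 should add that the analyst works on masked arm labels up to the lock. Section 9.4.7 already uses masking of this kind for a safety look, although it speaks of two arms and three labels are needed here.

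The cost is a short delay in releasing the key and minor documentation. Nothing changes for participants, visits or stimulation.
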